4.5.2. Exclusion Criteria

Subjects who meet any of the following exclusion criteria will be excluded from participation in this study:

1. Subjects who experienced a treatment-related AE or a serious AE (SAE) that precluded further treatment with ARQ-151 cream in studies ARQ-151-311 or ARQ-151-312 or ARQ-151-315.
2. Subjects that use any Excluded Medications and Treatments (see [Table 2](#)).
3. Subjects with skin conditions other than AD that would interfere with evaluations of the effect of the study medication on AD, as determined by the Investigator. Subjects with any condition on the treatment area which, in the opinion of the Investigator, could confound efficacy measurements (e.g., molluscum contagiosum).
4. Subjects with known genetic dermatological conditions that overlap with AD, such as Netherton syndrome.
5. Known allergies to excipients in ARQ-151 cream
[REDACTED]
6. Subjects who cannot discontinue the use of strong cytochrome P-450 CYP3A4 inhibitors e.g., indinavir, nelfinavir, ritonavir, clarithromycin, itraconazole, ketoconazole, nefazodone, saquinavir, suboxone and telithromycin during the study period.
7. Subjects who cannot discontinue the use of strong cytochrome P-450 CYP3A4 inducers e.g., efavirenz, nevirapine, glucocorticoids, barbiturates (including phenobarbital), phenytoin, and rifampin during the study period.

8. Known or suspected:
 - a. Severe renal insufficiency (defined as calculated creatinine clearance < 30mL/min)
Refer to the creatinine levels from the following visits:
 - ARQ-151-311/ARQ-151-312 studies: Screening Visit for subjects ages 6-11 and Baseline/Day 1 for subjects \geq 12 years old (for subjects 12-18 years old, if screening lab tests were collected within 3 weeks of Baseline/Day 1, screening results will be used)
 - ARQ-151-315 study: Screening Visit
 - b. moderate to severe hepatic disorders (Child-Pugh B or C)
 - c. history of severe depression, suicidal ideation or behavior
9. Females who are pregnant, wishing to become pregnant during the study, or are breast-feeding.
10. Subjects with any known serious medical condition (e.g., uncontrolled hypo- or hyper-thyroidism) or clinically significant laboratory abnormality that would prevent study participation or place the subject at significant risk, as determined by the Investigator.
11. Subjects with a history of chronic alcohol or drug abuse within 6 months of initiation of study medication.
12. Current or a history of cancer within 5 years with the exception of fully treated skin basal cell carcinoma, cutaneous squamous cell carcinoma or carcinoma in situ of the cervix.
13. Subjects and parent(s)/legal guardian(s) who are unable to communicate, read or understand the local language(s), or who display another condition, which in the Investigator's opinion, makes them unsuitable for clinical study participation.
14. Subjects who are family members of the clinical study site, clinical study staff, or sponsor, or family members of enrolled subjects (subjects enrolled in other studies of ARQ-151 cream) living in the same house.

4.6. Study Restrictions

4.6.1. Prohibitions and Concomitant Therapy

Prohibited medications and products are detailed in [Table 2](#) (Excluded Medications and Treatments).

Generally, the addition of new medications, including nonprescription medications, during the course of the study is discouraged. However, the short-term use of a medication may be authorized by the Investigator. The Investigator must make the decision to authorize the use of any such a medication only after consideration of the clinical situation, the potential for masking symptoms of a more significant underlying event, and whether the use of the medication will compromise the outcome or validity of the clinical investigation. Other medications may be authorized by the Investigator for conditions other than AD. If medication is required, the name,

strength, frequency, duration of use, and reason for use will be recorded in source documents and entered into the CRFs. Medications which have been used chronically by subjects, in particular statins and anti-hypertensives, are allowed for use during the study, except as prohibited in Table 2.

Non-medicated emollients, moisturizers and sunscreens can be applied to non-lesional and lesional skin. Subjects should maintain a stable moisturizer regimen and minimize changes to their moisturizer regimens and usual sunscreens.

Table 2: Excluded Medications and Treatments

Excluded Medications and Treatments
Biologics including dupilumab and investigational biologics
Systemic treatments that could affect AD; e.g. corticosteroids, retinoids, calcineurin inhibitors, hydroxycarbamide (hydroxyurea), methotrexate, cyclosporine, azathioprine, hydroxychloroquine, mycophenolate mofetil, or other immunosuppressive therapies.
PUVA or NBUVB phototherapy, tanning beds, other light emitting devices
Topical corticosteroids, calcineurin inhibitors, or Eucrisa®
Strong cytochrome P-450 CYP3A4 inhibitors e.g., indinavir, nelfinavir, ritonavir, clarithromycin, itraconazole, ketoconazole, nefazodone, saquinavir, suboxone and telithromycin
Strong cytochrome P-450 CYP3A4 inducers e.g., efavirenz, nevirapine, glucocorticoids, barbiturates (including phenobarbital), phenytoin, rifampin, and carbamazepine
Systemic antibiotics, except short courses, e.g., ≤ 15 days
Oral roflumilast (Daxas®, Daliresp®)
All other investigational drugs

Note:

- No rescue therapy is permitted per protocol.
- Eye / ear drop and nasal corticosteroid preparations are allowed. Inhaled corticosteroid preparations are allowed if used for a stable condition and at a stable dose.
- Non-medicated emollients, moisturizers and sunscreens can be applied to non-lesional and lesional skin. Subjects should maintain a stable moisturizer regimen and minimize changes to their moisturizer regimens and usual sunscreens.
- Concomitant other medications for chronic conditions (eg, NSAIDs, statins, anti-hypertensives) are permitted unless specifically prohibited in the Protocol.
- Topical antibiotics, topical antihistamines, or any other topical agents are not allowed to be applied to treated areas.

4.7. Treatment

4.7.1. IP Supplies, Packaging and Labeling

ARQ-151 cream will be supplied in 45 or 60 gram tubes. The tubes will be packaged in kits, containing multiple tubes of investigational product. The kit(s) dispensed to a subject will be labeled with a unique number.

The Sponsor will supply sufficient quantities of the study drug to each study site to allow for completion of this study.

Records will be made of the receipt and dispensing of the study drugs supplied. At the conclusion of the study, any used/unused study drugs will be returned to the Sponsor or designee, or destroyed, as per Sponsor instructions.

Refer to the most current version of the IP Handling Plan for details on accountability, storage, and management of ARQ-151 cream.

4.7.2. Blinding

This is an open label study, therefore the subjects, the Investigator, clinical personnel, and the sponsor will be aware of which treatment an individual subject receives.

4.7.3. Treatment Administration

Initial treatment with the IP in the ARQ-151-313 will occur on Day 1 (Day 29 from the preceding study). ARQ-151 cream 0.15% or ARQ-151 cream 0.05% is administered once daily (unless entering BIW maintenance therapy) as a topical product to cover the skin surface at an application rate of approximately 2 mg/cm².

At Day 1 visit, the study staff will redemonstrate to the subject/caregiver(s) how to apply ARQ-151 cream using the first tube from the kit that is assigned to the subject. Study site staff will be retrained to ensure a unit dose (a pea size unit of ARQ-151 cream will cover approximately 1% BSA) is properly squeezed from the tube and applied to atopic dermatitis lesion(s) as a thin film and rubbed in using the index and middle finger, rubbing in thoroughly but gently, until the ‘white’ has disappeared. The subject/caregiver will then practice squeezing a similar amount onto their index and middle finger and apply a thin film to other areas to be treated. At Day 1, the study staff will ensure that the subject/caregiver’s application technique is correct and that a thin layer is applied as instructed (which represents an application rate of approximately 2 mg/cm²).

Re-training will be conducted at subsequent visits as needed (i.e., if the returned tube(s) weighs substantially different than the expected weight).

For the first 4 weeks of study ARQ-151-313, all subjects will apply study medication QD in the areas identified and treated as per the body diagram in the preceding study (ARQ-151-311/312/315). Beginning at the Week 4 visit, any subject who achieves vIGA-AD of ‘0-clear’ as confirmed by the Investigator at a scheduled or unscheduled clinic visit, will switch to twice weekly (BIW) maintenance treatment. For maintenance therapy, study medication will be applied on two nonconsecutive days per week (e.g. Monday and Thursday) to areas commonly

and/or most recently affected by AD, and any areas where AD is developing. Subjects receiving maintenance treatment who experience AD worsening (signs and symptoms) for 1 week despite dosing twice weekly will phone the clinical study site, resume daily dosing, and complete the subject diary accordingly. The phone call (but not a clinic visit) is required to resume daily dosing. At clinic visits, subjects receiving maintenance treatment may continue twice weekly maintenance dosing if vIGA-AD is either '0-clear' or '1-almost clear'. Subjects will resume daily dosing if vIGA-AD ≥ 2 , and can resume daily dosing if signs/symptoms of AD are not adequately controlled with maintenance therapy despite vIGA-AD of '1-almost clear'.

Note:

- For daily dosing from Week 4 onwards, study medication should be applied to any areas where AD is active or developing, and areas commonly and/or most recently affected by AD.
- All subjects should apply medication each evening (unless on BIW maintenance therapy) except on Day 1 when medication application will be done on site. If the subject takes an evening shower/bath, the ARQ-151 cream can be applied as soon as the skin is nearly dry, but no later than 20 minutes before going to bed. Subjects are not to wash areas where ARQ-151 cream has been applied until at least 2 hours after study drug application.
- Caregivers should wash their hands with soap and water after applying IP to a child.
- Parents/guardians/caregivers who are pregnant, or women of childbearing potential who are trying to become pregnant, or who are breastfeeding, or planning to breastfeed during the study should avoid accidental exposure by either avoiding applying investigational product or by wearing gloves during its application.
- New lesions that develop during the study should be treated (except scalp). An unscheduled visit is not required for starting treatment of new lesions.

Each investigational product tube will be weighed prior to dispensing at the Day 1 visit and at each subsequent visit. Investigational product tubes must be returned by subjects at each study visit, both empty and full, and will be weighed. If the subject's actual use is substantially different than the expected use for the subject's BSA (see IP Handling Plan), the subject/caregiver will be retrained on the study drug application technique.

4.7.4. Treatment Compliance

Investigational product tubes will be weighed at each clinic visit.

Subjects/caregivers will complete a daily diary recording the date and time of each dose applied, any missed doses, and a comment section should the subjects have a comment, e.g., record potential AEs. Study site personnel will review the diaries and use the information to question the subject regarding compliance and AEs and then record appropriate information in source documents and complete Case Report Forms (CRFs). If a subject misses a dose, they should be instructed to return to the protocol investigational product administration schedule (i.e. if subject forgets a dose they should wait until that evening and apply as usual).

A subject will be considered compliant with the dosing regimen if the subject meets both of the following requirements:

- applies at least 80% of the expected applications during the study drug application period
- does not miss more than 3 consecutive doses

Compliance will be assessed by review of the dosing diary. Weight of investigational product applied (via dispensed and returned tube weights) will be measured.

If the diary shows less than 80% of expected applications (but not more than 3 consecutive missed doses), the subject is using too little study drug and retraining must be conducted and documented.

Compliance will be documented in source and in eCRF.

4.7.5. Removal of Subjects from Study Treatment

A subject may discontinue study treatment for any of the following reasons:

1. Occurrence of any medical condition or circumstance that, in the opinion of the Investigator, exposes the subject to substantial risk and/or does not allow the subject to adhere to the requirements for investigational product as per the Protocol.
2. Adverse Events as described in [Section 5.9](#) the Investigator must follow the subject until the AE resolves or satisfactorily stabilizes.
3. Treatment must be discontinued immediately in the event of a female subject's pregnancy.
4. Subject's decision to discontinue treatment with study drug.
5. C-SSRS ([Section 5.1.10](#)) indicative of suicidal ideation (score > 0).
6. PHQ-8 ([Section 5.1.7](#)) or modified PHQ-A ([Section 5.1.8](#)) score ≥ 15 if determined by Investigator in consultation with mental health professional.
7. CDI-2 ([Section 5.1.9](#)) raw total score of ≥ 32 if determined by Investigator in consultation with mental health professional.

4.7.6. Removal of Subjects from the Study

A subject may be removed from study participation for any of the following reasons:

1. Subject death.
2. Subject's decision to withdraw from study.
3. Subject is lost to follow-up. A subject will be considered lost to follow-up after three phone and three email attempts and documentation of a certified letter sent to the subject's address.

4. Requirement for use of prohibited concomitant medication after consultation with the Sponsor and Medical Monitor.
5. Subject's repeated failure to comply with protocol requirements or study related procedures.
6. The subject interrupts trial study drug application for more than 50% of scheduled doses.
7. Termination of the study by the Sponsor, FDA, or other regulatory authorities.

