5.7. Adverse Events

5.7.1. Adverse Event Definition

An AE is defined as any untoward medical occurrence associated with the use of a drug in humans, whether or not considered drug related. An AE can therefore be any unfavorable and unintended sign (including an abnormal laboratory finding), symptom, or disease temporally associated with the use of a medicinal (investigational) product, whether or not related to the medicinal (investigational) product.

A treatment emergent adverse event (TEAE) is defined as an AE that started post application of study medication at the Day 1 visit of study ARQ-151-313 or was present at treatment initiation but worsened during treatment, through study completion.

The definition of AEs includes worsening of a pre-existing medical condition. Worsening indicates that the pre-existing medical condition has increased in severity, frequency, and/or duration or has an association with a worse outcome. When recording such events, provide descriptions that the pre-existing condition has changed (eg, worsening hypertension for a subject with pre-existing hypertension). A pre-existing condition that has not worsened during the study or involves an intervention, such as elective cosmetic surgery or a medical procedure while on study, is not considered an AE.

Progression of atopic dermatitis including new or worsening of anticipated clinical signs or symptoms, which are collected as clinical efficacy variables and assessed as unequivocally associated with the disease progression and /or lack of efficacy, should NOT be reported as adverse events unless the disease progression is greater than anticipated in the natural course of the disease.

In general, abnormal laboratory findings without clinical significance (based on the investigator's judgment) are not to be recorded as AEs. However, abnormal laboratory findings that result in new or worsening clinical sequelae, or that require therapy or adjustment in current therapy, are considered AEs. Where applicable, clinical sequelae (not the laboratory abnormality) are to be recorded as the AE.

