5.5 Derived Variables

All questionnaire scores will be derived by Biostatistics in the ADaM datasets using the formulas defined below, even if calculated scores are present in the EDC database. All pre-calculated scores will be ignored for analysis.

- With the following exception, vIGA-AD Score of Clear (0) or Almost Clear (1) = vIGA-AD of ‘Clear’ (0) or ‘Almost Clear’ (1). The exception is that for subjects who discontinued early from study due to an AE or lack of efficacy, the subject will be considered as not having a vIGA-AD score of Clear (0) or Almost Clear (1) for all pre-specified analysis visits (refer to Section 5.4) for which the subject’s day of last dose falls within or is before the start of the analysis visit window.
- With the following exception, vIGA-AD Success = vIGA-AD of ‘Clear’ (0) or ‘Almost Clear’ (1) plus at least a 2-grade improvement from baseline. The exception is that for subjects who discontinued early from study due to an AE or lack of efficacy, the subject will be considered as not having a vIGA-AD success for all pre-specified analysis visits (refer to Section 5.4) for which the subject’s day of last dose falls within or is before the start of the analysis visit window. vIGA-AD Success will be derived for both the Primary and OLE baselines (refer to Section 5.2)
- Date of last contact = the latest of last study visit date, last dose date, end-of-study date and end-of-treatment date.
- Post-OLE Week 4 study duration (days): The duration can be represented as End Date – Start Date +1. The start date of the Post-OLE Week 4 interval will be the date of the OLE Week 4 visit or OLE Day 29 if the subject missed the OLE Week 4 visit. The end date will be the date of last contact. This endpoint will be calculated only for subjects who enter the post-OLE Week 4 study period.
- Duration (days) of the first BIW dosing will be calculated from the first BIW dosing to the start of the succeeding QD dosing interval. Subject’s last contact date will be used to censor

 Innovaderm Research	STATISTICAL ANALYSIS PLAN, Final Version 1.0
Protocol Number: ARQ-151-313	Sponsor: Arcutis Biotherapeutics, Inc.

this endpoint (time-to-event analysis) or as the end date of this duration (analyzed as a continuous endpoint) for subjects who do not revert to a QD dosing regimen after the first BIW dosing. This endpoint will be calculated only for subjects who enter the post-OLE Week 4 study period with at least one BIW dosing interval.

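### In the vIGA-AD analyses, exits because prohibited AD treatment is needed are not tied to the lack-of-efficacy rule, and no analysis handles prohibited AD treatment used on study

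*Protocol*

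**What the plan says.** **Protocol.** Section 4.6.1 states "No rescue therapy is permitted per protocol". Its Table 2 excludes "Topical corticosteroids, calcineurin inhibitors, or Eucrisa", along with biologics, phototherapy and systemic treatments that could affect AD. Item 4 of the reasons for removal from the study (4.7.6) is "Requirement for use of prohibited concomitant medication after consultation with the Sponsor and Medical Monitor". The same list has the subject's own "decision to withdraw from study", and the list for stopping treatment (4.7.5) has the subject's "decision to discontinue treatment with study drug". Neither list names lack of efficacy. Under 5.7.1, AD progression put down to the disease itself or to insufficient effect "should NOT be reported as adverse events unless the disease progression is greater than anticipated in the natural course of the disease".

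**SAP.** Section 5.5 defines vIGA-AD 0/1 and vIGA-AD success by the observed score, with one exception. It applies "for subjects who discontinued early from study due to an AE or lack of efficacy", and scores the affected visits as non-response. Section 6.2.1 removes data before imputation for the same two reasons only. Other withdrawals keep their last available data. Missing scores are imputed by predictive mean matching (PMM) on stratum, parent-study treatment and earlier vIGA-AD scores. Section 12.2.1 makes this the main analysis. Sections 6.2.2 and 12.2.2 add two sensitivity analyses: non-responder imputation (NRI) of missing endpoint values, and observed cases.

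**The concern.** A subject whose AD is not controlled and who needs a topical steroid has no permitted rescue, and the flare will usually not be an AE. Item 4 of 4.7.6 describes that subject's exit directly. If the exit is recorded under that reason, neither limb of the SAP rule applies. The later visits are then filled in from subjects with similar earlier scores who stayed on roflumilast, although the reason for leaving may itself be treatment failure.

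A second subject starts the topical steroid, stays on study and is clear at the next visit. That score is observed, so it counts as a response on roflumilast.

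Both routes push the reported vIGA-AD proportions upward. What is at stake is the accuracy of the descriptive long-term response rates. No hypothesis test is involved, and the primary endpoints are safety.

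**Working it through.** The documents give no vIGA-AD response, dropout or prohibited-medication rate, so there is no plan figure to reproduce. The check has two parts: tracing the rules, and sizing the effect under stated assumptions.

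**1. Which rule reaches which subject**

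| Situation | Main analysis (MI) | NRI | Observed cases |
|---|---|---|---|
| Exit coded AE or lack of efficacy | non-response | non-response | non-response (5.5 exception) |
| Exit under 4.7.6 item 4, not coded as lack of efficacy, later visits missing | imputed by PMM | non-response | left out |
| Stays on study, prohibited AD treatment started, vIGA-AD 0 or 1 observed | counted as observed | counted as observed | counted as observed |

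The PMM model has no term for exit reason or concomitant medication. NRI changes only missing values, so it cannot reach the third row. The SAP defines no per-protocol set (Section 4). Prohibited use appears only among concomitant medications (Section 10) and protocol deviations (7.2).

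**2. Formula**

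Compared with scoring these subjects as non-responders, the response proportion is higher by

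f × q + u × r

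- f: share leaving because prohibited medication is needed for AD and not coded as lack of efficacy
- q: share of their imputed scores that are 0 or 1
- u: share who start a prohibited AD treatment and stay
- r: share of those with an observed 0 or 1 afterwards

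All four are assumptions.

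**3. Exits (f × q)**

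A value for q came from an illustrative PMM run on a simulated five-grade score. It used N = 1500, 25 imputations and 5 nearest donors, with a marginal 0/1 rate of about 50%. Exits were drawn from subjects with a score of 2 or more at their last visit, and the next three visits were missing. Visit-to-visit correlation of the latent score was 0.5, 0.7 or 0.85. Stratum and treatment were left out. Each cell shows q at the final visit, then f × q in percentage points.

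| f | correlation 0.5 | 0.7 | 0.85 |
|---|---|---|---|
| 2% | 46.9%; 0.94 | 37.6%; 0.75 | 35.1%; 0.70 |
| 5% | 48.9%; 2.45 | 41.6%; 2.08 | 28.2%; 1.41 |
| 10% | 45.5%; 4.55 | 40.1%; 4.01 | 26.8%; 2.68 |

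So even subjects who left with a score of 2 or more were imputed as 0/1 in 27% to 49% of draws.

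**4. On-study use (u × r)**

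- 1% × 20% = 0.2 points
- 5% × 40% = 2.0 points
- 10% × 60% = 6.0 points

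**5. Scale**

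The Wilson 95% half-width at a proportion of 50% is 2.5 points with n = 1500. It is 3.2 points with n = 950, which is 1500 less the roughly 275 + 275 = 550 planned for Cohort-Week 24. SAP Section 5 reports rollovers from 311/312 and from 315 separately, so the actual groups are smaller and their intervals wider.

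**The case against.** **The exit part depends on coding that cannot be seen.** The SAP plainly expects lack of efficacy to be a recorded discontinuation reason, and SAP 7.1 tabulates such reasons. The protocol lists say why a subject may be removed; they are not the eCRF code list. If sites code AD-driven exits as lack of efficacy, the rule already works. This stands: the documents show an undefined mapping, not that such failures will be imputed.

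**NRI is already planned.** It scores the missing visits after any exit as non-response. This stands for the exits, but not for on-study use.

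**PMM is not naive.** It conditions on earlier scores, and an early-termination score that falls in an open visit window can be used. A flaring subject is therefore predicted from poor scores. This is right, and the simulated q reflects it. The simulated exits also depended only on observed scores, so the differences above measure a choice of scoring and do not prove that missing at random fails.

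**Using observed scores whatever else is taken is a recognised strategy.** True, but the SAP does not say that it chose this strategy, and no planned analysis shows how much the result depends on it.

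**Stronger readings that the documents do not support.** A reader might infer that item 4 is the only way out for an AD failure. It is not: subjects can leave or stop by their own decision, and worsening greater than anticipated can be an AE. Item 4 also covers prohibited medication unrelated to AD, such as CYP3A4 inhibitors. A reader might also infer that the plan contradicts the parent studies' estimand, which SAP 6.2.1 cites. The parent SAPs are not among the documents, so this cannot be judged. Finally, it would be wrong to apply an imputed response rate to subjects who stay, because their scores are observed.

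**Conclusion.** The point holds as a gap in the SAP. The mapping from protocol exit reasons to lack of efficacy is missing, so an AD-driven exit under item 4 can fall to PMM imputation in the main analysis. The on-study gap is firmer: no exit coding can close it, and MI, NRI and observed cases all count the score as it stands.

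Under the assumed inputs, the exits overstate response by 0.7 to 0.9 points at 2%, 1.4 to 2.5 at 5% and 2.7 to 4.6 at 10%, relative to counting them as failures. On-study use adds u × r, for example 2.0 points at 5% and 40%. The upper part of this range is similar to the half-widths shown for scale. With few such subjects, or with exits coded as lack of efficacy, the exit effect is small or absent.

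The consequence is limited to descriptive secondary estimates. The change should still be made, because it is cheap and removes a one-directional doubt about the response rates.

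**What to change.** 1. In SAP 5.5 and 6.2.1, state that discontinuation because prohibited medication was needed for AD is treated as lack of efficacy. Identify these subjects from the disposition and concomitant-medication records together, so that item 4 exits for other conditions are not swept in.
2. In SAP 12.2.2, add a sensitivity analysis of both vIGA-AD endpoints that sets response to no at visits after the start of a Table 2 treatment taken for AD.

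The cost is SAP wording and one derived flag, using records the study already collects. Study conduct does not change. The reported response rate may be slightly lower.
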